STUDY PROTOCOL

STUDY ON THE SAFETY OF ADMINISTERING ISONIAZID TO SYSTEMIC LUPUS ERYTHEMATOSUS PATIENTS TO PREVENT TUBERCULOSIS

Unique Protocol ID: IPD-202402.01

Document Date: August 1st 2022

NCT Number: N/A

Researcher:

**[name], dr., Sp.PD-KR, M.Kes
(8830960018)**

[name], dr., PhD (0011056602)

**[name], dr., Sp.PD-KPTI, PhD
(8849720016)**

[name], dr., Sp.PD

PADJADJARAN UNIVERSITY

2024

STUDY PROTOCOL

STUDY ON THE SAFETY OF ADMINISTERING ISONIAZID TO SYSTEMIC LUPUS ERYTHEMATOSUS PATIENTS TO PREVENT TUBERCULOSIS

Researcher:

[name], dr., Sp.PD-KR., M.Kes - Division of Rheumatology and Immunology, Department of Internal Medicine, Padjajaran University, Hasan Sadikin Hospital Bandung.

[name], dr, Sp.PD-KPTI, PhD - Division of Tropical and Infectious Diseases, Department of Internal Medicine, Padjajaran University, Hasan Sadikin Hospital Bandung.

[name], dr., PhD - Division of Molecular Biology, Department of Biomedical Sciences, Padjajaran University, Hasan Sadikin Hospital Bandung.

[name], dr., Sp.PD - Department of Internal Medicine, Krida Wacana Christian University.

Aim

This study aims to prove that the administration of Isoniazid (INH) in the prevention of Tuberculosis (TB) in patients with Systemic Lupus Erythematosus (SLE) is safe against liver toxicity and disease recurrence.

Research Design

An open-label, randomized, controlled, prospective cohort study evaluating two groups of SLE patients, those receiving INH and pyridoxine for nine months and those not receiving both drugs. Signs and symptoms of drug-induced hepatotoxicity and degree of SLE disease activity were assessed monthly for the first three months (months 1/2, 1, 2, and 3), and then continued every three months for up to one year (months 6, 9, and 12).

Introduction

Systemic Lupus Erythematosus (SLE) is a highly complex chronic autoimmune disease that affects multiple organs.¹ The course of the disease is influenced by many things, one of which is infection.² SLE patients are more susceptible to infections, due to their disease activity as well as the use of immunosuppressant drugs and glucocorticoids.³ One of the infections that mainly affects SLE patients is Tuberculosis (TB) infection,⁴ especially patients living in Asian areas that are endemic to TB.⁵

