Types of damage in drug-induced hepatotoxicity²⁸	Type of damage: 
• Hepatocellular (SGPT ≥ 3 upper limit of normal values and $R \geq 5$).• Cholestatic (ALP ≥ 2 upper limit of normal value and $R \leq 2$).• Mixed (SGPT ≥ 3 upper limit of normal, ALP ≥ 2 upper limit of normal, and $2 < R < 5$).	Laboratory examination	According to the type of damage	Nominal
Severity of drug-induced hepatotoxicity²⁸	
• Grade 0 (No Liver Injury): the patient can tolerate the drugs and there are no signs and symptoms of hepatotoxicity.• Grade 1 (Mild Liver Injury): elevated SGPT and/or ALP values, total bilirubin < 2.5 upper limit of normal (2.5 mg/dL or 42.75 $\mu\text{mol/L}$), INR < 1.5. Most patients show adaptive processes to liver damage. It may be accompanied or without symptoms, such as fatigue, nausea, anorexia, right upper abdominal pain, jaundice, itching, skin redness, or weight loss.• Grade 2 (Moderate Liver Injury): elevated SGPT and/or ALP values,	History review, physical examination, laboratory examination	As per grade	Ordinal

with total bilirubin ≥ 2.5 upper limit of normal or INR ≥ 1.5 . Symptoms and signs of impaired liver function become more apparent.

- *Grade 3 (Severe Liver Injury):* elevated SGPT and/or ALP, total bilirubin ≥ 5 upper limit of normal (5 mg/dL or 85.5 μ mol/L) with or without INR ≥ 1.5 . Symptoms and signs of hepatic impairment are obvious, indicating the need for hospitalisation. There are no signs and symptoms of hepatic encephalopathy.
- *Grade 4 (Acute Liver Failure):* evidence of blood clotting disorders with INR ≥ 1.5 or PTA $<40\%$, signs and symptoms of hepatic encephalopathy, and total bilirubin values ≥ 10 upper limit of normal (10 mg/dL or 171 μ mol/L) or an increase in total bilirubin values ≥ 1.0 mg/dL (17.1 μ mol/L) per day for 26 weeks after the onset of drug-induced hepatotoxicity. Patients may develop ascites and other organ dysfunction.
- *Grade 5 (Lethal):* death caused by drug-induced hepatotoxicity.

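### As written, Grade 4's rate-of-rise criterion for liver failure can never apply on its own, and encephalopathy with bilirubin below 10 x ULN drops to Grade 2

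*Protocol*

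**What the plan says.** The row on severity of drug-induced hepatotoxicity in the Protocol's Variables table defines Grades 0 to 5 and declares the variable ordinal. The follow-up CRF in Appendix 2 has a tick-box for each grade. Three grades matter here.

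- **Grade 2 (moderate):** raised SGPT or ALP "with total bilirubin ≥ 2.5 upper limit of normal or INR" of at least 1.5. The clinical wording is "Symptoms and signs of impaired liver function become more apparent". No upper bilirubin limit is given, and encephalopathy is not excluded.
- **Grade 3 (severe):** raised SGPT or ALP and bilirubin of at least 5 x ULN, whatever the INR. It adds: "There are no signs and symptoms of hepatic encephalopathy".
- **Grade 4 (acute liver failure):** "evidence of blood clotting disorders with INR ≥ 1.5" or PTA below 40%, encephalopathy, "and total bilirubin values ≥ 10 upper limit of normal (10 mg/dL", "or an increase in total bilirubin values ≥ 1.0 mg/dL" "per day for 26 weeks after the onset of drug-induced hepatotoxicity".

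The two bilirubin criteria in Grade 4 are alternatives. Either one is enough, given the clotting disorder and encephalopathy.

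**The concern.** A rate-of-rise criterion placed beside an absolute threshold is there to pick up patients whom the threshold misses, namely those who are deteriorating fast but are still below it. As written, this one asks for a daily rise sustained over half a year, so it cannot do that job. Grade 3 is closed to anyone with encephalopathy, so these patients do not land one grade lower either.

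The Aim is to show that isoniazid is safe for the liver. A rule that records liver failure with encephalopathy as moderate injury errs in the direction of that claim. It would also be easy to miss, because the case still receives a valid grade.

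**Working it through.** **Inputs**, all from the severity row of the Variables table: bilirubin thresholds of 2.5, 5 and 10 x ULN with their unit equivalents; a rise of 1.0 mg/dL per day; 26 weeks; INR of 1.5; and the Grade 3 exclusion of encephalopathy.

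**1. The table's own figures.** With a factor of 17.1 from mg/dL to μmol/L: 1.0 x 17.1 = 17.1; 2.5 x 17.1 = 42.75; 5 x 17.1 = 85.5; 10 x 17.1 = 171. All four agree with the table. Since 10 x ULN is equated with 10 mg/dL, the implied ULN is 10/10 = 1 mg/dL.

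**2. Rise required by the second alternative, read literally.** 26 weeks x 7 days = 182 days, and 182 x 1.0 mg/dL = 182 mg/dL. That is 182 x 17.1 = 3112 μmol/L, or 182 times the implied ULN.

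**3. Time to meet the first alternative at that rate.** Days = (10 - starting value) / 1.0, rounded up.

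| Starting bilirubin (mg/dL) | Days to reach 10 mg/dL |
|---|---|
| 0.5 | 10 |
| 1.0 | 9 |
| 2.5 | 8 |
| 5 | 5 |
| 9.9 | 1 |

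Anyone who could complete 182 days of such a rise would have met the first alternative by about day 10. The second adds no patient.

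**4. Grade assigned.** Take a living patient with raised SGPT or ALP and INR 1.6, apply each grade as worded, and assign the highest grade met.

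| Bilirubin (x ULN) | Without encephalopathy | With encephalopathy |
|---|---|---|
| 1 | 2 | 2 |
| 2.5 | 2 | 2 |
| 4 | 2 | 2 |
| 5 | 3 | 2 |
| 7 | 3 | 2 |
| 9.9 | 3 | 2 |
| 10 | 3 | 4 |
| 12 | 3 | 4 |

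From 5 x ULN to just under 10 x ULN, adding encephalopathy to an otherwise identical patient lowers the grade from 3 to 2. Below 5 x ULN the grade does not change, but an encephalopathic patient with a clotting disorder still ranks under a non-encephalopathic patient at 5 x ULN.

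If the clotting disorder rests on PTA alone and INR is below 1.5, the encephalopathic patient meets Grade 2 from 2.5 x ULN and only Grade 1 below that, until Grade 4 opens at 10 x ULN.

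**5. How much of this comes from the 26-week phrase.** Only the fast-rising patients. Take one with encephalopathy, INR of at least 1.5 and bilirubin of 6 mg/dL rising by less than 1.0 mg/dL per day. That patient is outside Grade 4 however the phrase is worded, and outside Grade 3 because of its exclusion. That part of the gap comes from how Grades 3 and 4 meet.

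**The case against.** The most natural defence is that the phrase is a slip: 26 weeks was meant as a window after onset, and any sensible assessor would read it so. That may be right. But the sentence gives a duration, nothing else in the Protocol corrects it, and the guideline the table cites is not at hand. The intended meaning cannot be settled from this document.

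Second, the event would be recorded elsewhere. The scale for unexpected events in the same table has a life-threatening Grade 4 that does not depend on bilirubin, and the follow-up CRF lets the assessor tick acute liver failure directly. This stands as mitigation. It also means that one patient could be life-threatening on one scale and moderate on the other.

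Third, visits are at half a month, monthly to month 3, "and then continued every three months for up to one year (months 6, 9, and 12"). A daily rise cannot be seen from visits so far apart, so the criterion would depend on unscheduled tests however it is worded. This stands, and it limits how often the phrase would matter. It does not make the phrase correct.

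Fourth, the severity grade carries no analysis. Data Analysis names the increase in SGOT/SGPT and SLEDAI activity, and hepatotoxicity itself is a yes/no variable based on SGOT/SGPT above twice the ULN with recovery once the drug is stopped. This stands in full and sets the size of the point.

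**Conclusion.** The point holds as a drafting error in a recorded safety variable. Grade 4's second bilirubin alternative requires 182 mg/dL and is redundant. Encephalopathy with a clotting disorder and bilirubin below 10 x ULN is shut out of Grades 3 and 4, and the resulting order is wrong between 5 and 10 x ULN. The practical effect is on the description of rare events: few if any are to be expected in 60 patients, and no stated comparison changes.

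Three stronger readings are tempting, and the Protocol does not support them.

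- A reader might infer that Grade 4 cannot be reached. It can, through 10 x ULN.
- A reader might infer that these patients fit no grade. With raised SGPT or ALP and INR of at least 1.5 they meet Grade 2, so they are under-graded, not ungraded. An empty cell would follow only from a Grade 2 limit that is not written, or from SGPT and ALP both being normal.
- A reader might infer that one such case would decide the trial's main safety outcome. No such decision rule is stated. One event in 30 against none in 30 gives an uncorrected chi-square of 60 x (1 x 30 - 29 x 0)² / (30 x 30 x 1 x 59) = 1.017, p = 0.31.

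The conclusion assumes that the grades are applied as worded, that the highest grade met is assigned, and that ULN is 1 mg/dL as the table implies.

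**What to change.** Two edits to the severity row of the Variables table:

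1. Check the 26-week phrase against the guideline the table cites, and state whether it is a time window after onset or a duration of the rise.
2. Reconcile the wording of Grades 2, 3 and 4 so that encephalopathy with coagulopathy cannot be graded below Grade 3. Correcting the phrase alone would leave the slower-rising patients described above in Grade 2.

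The thresholds themselves should come from the cited guideline and the sponsor's hepatology advice; this review proposes none. The cost is a few sentences in one table row, and the CRF tick-boxes need no change. If any case with encephalopathy has already been recorded, its grade should be checked against the corrected wording.

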Unexpected events²⁹	
 • Grade 1 Mild; asymptomatic or mild symptoms only; clinical observation or diagnosis only; intervention not indicated. • Grade 2 Moderate; minimal, local or non-invasive interventions are indicated; limitation of daily activities based on age. • Grade 3 Severe or medically significant, but not life threatening; indication for hospital admission; limitation of independent daily activities. • Grade 4 Life-threatening; indication for rapid/immediate intervention. • Grade 5 Lethal; associated with an adverse event. 	History review, physical examination, laboratory examination	As per grade	Ordinal
Acid Fast Bacilli (AFB)³⁰	Staining technique to see acid fast bacilli (Mycobacterium tuberculosis) from the sample taken	Laboratory examination	Positive/negative	Nominal
Rapid Molecular Test (RMT)³¹	Rapid PCR (Polymerase Chain Reaction) testing using the GeneXpert platform that can detect TB bacteria	Laboratory examination	Positive/negative	Nominal

Research Duration and Time

This research was conducted from August 2022 to December 2024.

Sample size calculation

The sample size calculation was carried out based on INH prophylaxis studies conducted in HIV patients, obtained the risk of *drug reaction* events of RR 1.2, so that with a confidence level of 95%, power 80%, and effect size 0.5, the sample

size of each group was 27 people, plus 10% to 30 people. Thus, the total number of patients involved is 60 people who will be divided into two groups.

Data Analysis

This study was conducted to assess the safety of INH drug administration in SLE patients by analyzing the increase in SGOT/SGPT values and assessing SLE disease activity measured using SLEDAI. Both will be assessed after two weeks of drug or placebo administration, followed by monthly for the first three months (months 1, 2, 3), then every three months until one year (months 6, 9, 12). Statistical tests used were t-test and/or chi-square by comparing two treatment groups. Results were considered significant when the p value was ≤ 0.05 . Data processing was performed with SPSS version 26 and Stata version 13.

Outputs

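### The stated inputs do not give 27 per group for a two-group test; if effect size 0.5 means Cohen's d (two-sided), power is about 44%, and RR 1.2 cannot reach 80% two-sided at this size

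*Protocol*

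**What the plan says.** The Sample size calculation section takes the relative risk of drug reactions from INH prophylaxis studies in HIV patients. It goes on from drug-reaction "events of RR 1.2, so that with a confidence level of 95%, power 80%, and effect size 0.5, the sample" size follows. The result is given as "size of each group was 27 people, plus 10% to 30 people", and "the total number of patients involved is 60 people who will be divided into two groups".

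The Data Analysis section fixes the tests that this number has to serve: "Statistical tests used were t-test and/or chi-square by comparing two treatment groups". On the significance level it says: "Results were considered significant when the p value was ≤ 0.05".

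The protocol does not say what kind of effect size 0.5 is, whether the test is one- or two-sided, which outcome it refers to, or what control risk or standard deviation was assumed.

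**The concern.** This is a completed calculation, with inputs and a result, so it can be checked. A standardised difference of 0.5 between two independent groups is known to need roughly 60 patients or more per group at these error rates, and 27 is less than half of that. It is also unclear how a relative risk of 1.2 becomes an effect size of 0.5.

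The Aim section sets out to prove that INH is safe with respect to liver toxicity and disease recurrence, and the test is one of difference at the 5% level. A non-significant result may therefore be read as evidence of safety. How much reassurance it gives depends on the power, so an overstated power understates how large a harm could have been missed.

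**Working it through.** **Inputs.** Alpha 0.05 (95% confidence, p ≤ 0.05), power 0.80, effect size 0.5, RR 1.2, 27 per group (30 with the allowance), all from the Sample size calculation and Data Analysis sections. Sidedness is not stated, so both are tried. Control risks below are my assumptions.

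**1. The allowance.** 27/0.9 = 30, and 27 × 1.1 = 29.7, which rounds up to 30. This step is sound.

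**2. The 27, by two-group reading of 0.5** (per group, 80% power). With (1.960 + 0.842)² = 7.849 two-sided and (1.645 + 0.842)² = 6.183 one-sided:

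| Reading of 0.5 | Formula | Two-sided | One-sided |
|---|---|---|---|
| Cohen's d | 2 × 7.849/0.5² = 62.8; exact t 63.8 | 64 | 51 |
| Cohen's h | 2 × 7.849/0.5² = 62.8 | 63 | 50 |
| Cohen's w, 1 df | 7.849/0.5² = 31.4 in total | 16 | – |
| Cohen's f (d = 1.0) | exact t 16.7 | 17 | – |
| Risk difference, control risk 0–50% | pooled two-proportion formula, 10.5 to 14.5 | 11–15 | – |

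A continuity correction moves the last row to 15–19. None gives 27.

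**3. Power if 0.5 is Cohen's d.** With 27 per group the noncentrality is 0.5 × √(27/2) = 1.837. The normal approximation gives Φ(1.837 − 1.960) = 45.1%; the noncentral t gives the exact values:

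| Evaluable per group | Two-sided | One-sided | d detectable at 80%, two-sided |
|---|---|---|---|
| 27 | 43.8% | 56.7% | 0.78 |
| 30 | 47.8% | 60.6% | 0.74 |

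**4. From RR 1.2 to 0.5.**
- For h, solving 2·arcsin√(1.2p) − 2·arcsin√p = 0.5 gives a control risk p = 0.793. RR 1.2 equals h = 0.5 only if about 79% of controls have the event.
- For w, the largest value that RR 1.2 allows is at control risk 1/1.2 = 0.833 and INH risk 1.00, with mean risk 0.917: w = (0.167/2)/√(0.917 × 0.083) = 0.30. It never reaches 0.5.

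**5. RR 1.2 as the target itself.** The pooled two-proportion formula (two-sided 5%, 80% power) and exact enumeration of the uncorrected chi-square (two-sided) give:

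| Control risk (assumed) | n per group for 80% | Exact power, 27 per group |
|---|---|---|
| 10% | 3,841 | 6% |
| 20% | 1,683 | 7% |
| 50% | 388 | 10% |
| 80% | 64 | 48% |
| 83.3% (INH risk 100%) | 42 | 68% |

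Over control risks from 1% to the 83.3% limit, the last row is the maximum. With 30 per group the maximum is 76%. One-sided, exact power reaches 80% only from a control risk of about 82.7% (27 per group) or 82.2% (30 per group), that is, when about 99% of INH patients have the event.

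**The case against.** The strongest reply is that 44% rests on a metric the protocol does not name. The only anchor in the sentence is a relative risk, and hepatotoxicity and relapse are categorical in the Variables table. If 0.5 were w or f, 27 per group would give about 96% or 95% power. This is right as far as it goes: the 44% is conditional on d. But the w, f and risk-difference readings give 11 to 17 per group (at most 19 with a continuity correction), not 27. RR 1.2 cannot reach w = 0.5, and the protocol does plan a t-test. The failure to reproduce 27 does not depend on choosing d.

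Second, RR 1.2 may be background and not the effect to be detected. The wording links the two, but not clearly. If it is only background, it cannot also justify the 27.

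Third, 27 can be reached in other ways. A one-sided one-sample or paired t-test with d = 0.5 needs 26.1, so 27. That may be where the number came from, but it is not the planned between-group comparison. Averaging six visits with an assumed correlation of 0.3 gives 63.8 × (1 + 5 × 0.3)/6 = 26.6, but the protocol states neither that analysis nor a correlation. The readings above are thus not exhaustive; these routes need a different design or unstated inputs.

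Finally, a small safety study is legitimate. I agree. The objection is to the power claimed for it, not to its size.

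**Conclusion.** The concern holds. The 27 per group does not follow from 95% confidence, 80% power and effect size 0.5 for the planned two-group tests, under any standard reading tried. If 0.5 is Cohen's d, the miss rate for that effect with 27 evaluable per group is 100 − 43.8 = about 56% two-sided, or about 43% one-sided, against the 20% claimed. For RR 1.2, a two-sided 5% chi-square stays below 80% power at every control risk with 27 or 30 per group. The one-sided exception needs nearly every INH patient to have the event.

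This must be fixed, because it is the only justification given for the sample size and it bears directly on how a null safety result is read.

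**What to change.** Keep the 60 patients and rewrite the Sample size calculation section:

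- Delete the claim of 80% power at effect size 0.5 and its derivation from RR 1.2.
- Name the effect-size metric and the sidedness for whatever power statement remains.
- State that, for a two-sided 5% t-test, 27 evaluable per group gives 80% power only for a standardised mean difference of about 0.78, and about 44% for 0.5.
- If precision for binary outcomes is added, use the same n and label the risks as assumptions. At an assumed 5% or 10% in both groups, the Wald 95% half-width for the risk difference is 1.96 × √(2p(1 − p)/27), about 12 or 16 percentage points. Say that this is rough, since only 27 × 0.05 = 1.35 to 27 × 0.10 = 2.7 events per group are expected. The Newcombe interval with 1, 2 or 3 events of 27 in each group is about ±15, ±17 or ±18 points.

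The cost is one reworded paragraph and a less favourable power figure. No patients, visits or tests change. The Research Duration section places conduct in August 2022 to December 2024, so correcting the justification is more practical than enlarging the study, and the results should be read against the corrected figures.

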- SLE patients who are in remission or low *disease activity state (LLDAS)*, with a history of stable SLE treatment in the last three months and have good liver function,
- Agree to fully participate in this study.

Exclusion Criteria

- SLE patients who have previous liver dysfunction, including hepatitis B or hepatitis C,
- SLE patients who have a history of allergy to INH,
- SLE patients with malignancy,
- SLE patients who are pregnant.

Variables

VARIABLES	DEFINITION	ASSESSMENT	OUTPUTS	DATA TYPE
Systemic Lupus Erythematosus (SLE)	ACR 1997 or SLICC 2012 criteria ^{22,23}	History review, physical examination, laboratory examination	Yes/No	Nominal
Age	Age at the time of study	History review	Year	Numerical
Duration of SLE	Duration from diagnosis of SLE to inclusion in the study.	History review and medical record confirmation	Month	Numerical
Isoniazid (INH) preventive therapy	INH 5 mg/kg/day, max 300 mg/day for nine months	History review	Yes/No	Nominal
Tuberculosis	Active TB.	History review, physical examination, Chest X-Ray, and/or AFB/RMT examination.	Yes/No	Nominal
SLE disease activity²⁵	Based on the SLE disease activity index (SLEDAI-2K) score: 
 • 0 = remission • 1-5 = mild • 6-11 = moderate • ≥ 12 = severe 	History review, physical examination, laboratory examination	As per score	Nominal
Changes in SLE disease activity²⁶	Based on change in SLE disease activity index (SLEDAI-2K) score. Change in score: 
 • increased ≥ 3 = relapse • decreased ≥ 3 = improved • increased but < 3 = active persistent 	History review, physical examination, laboratory examination	As per score	Nominal
Drug-induced hepatotoxicity (INH)	Increase of more than twice the upper limit of normal SGOT/SGPT values and improvement after drug withdrawal ²⁷	History review, physical examination, laboratory examination	Yes/No	Nominal

R value²⁸	Values used to distinguish the type of damage in drug-induced hepatotoxicity. $R = (\text{SGPT value} / \text{upper limit of normal SGPT value}) / (\text{ALP value} / \text{upper limit of ALP value}).$	Laboratory examination	As per the result value	Numerical

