 Fever  Malaise  Fatigue  Abdominal Pain  Nausea	Ht	
 Vomiting  Icteric	Leukocytes	
 Others:	Platelets	
Physical Examination	Count	Basophils
		Eosinophils
		Neut Rod
		Neut Segment
		Monocytes
		Lymphocytes
	Type	ESR
		SGOT
		SGPT
		Creatinine
	Urinalysis	Proteinuria
		Erythrocytes
		Leukocytes
		Cylinders

SLEDAI Score:

SLEDAI Total Score: 0 (Remission) 1-5 (Mild) 6-11 (Moderate) ≥ 12 (Severe)
SLE Disease Activity: Relapse Improving Persistently Active Remission

Elevated SGOT/SGPT \geq 2x Upper limit of normal values: Yes No

Liver function disorders: Hepatocellular Cholestatic Mixed

Severity: 0 (*No Liver Injury*)

- 1 (*Mild Liver Injury*)
- 2 (*Moderate Liver Injury*)
- 3 (*Severe Liver Injury*)
- 4 (*Acute Liver Failure*)
- 5 (*Lethal*)

Management of Drug-Induced Hepatotoxicity

INH discontinue Continue INH Administration
 Other medications:

Drug-induced hepatotoxicity outcomes

**CRF INH Safety Study in SLE Patients:
SLE recurrence**

Subject Number_____

Full Name: _____ Gender: F / L

Date of Birth (day/month/year): _____ / _____ / _____ Tel/Phone: _____

Visit _____ (months from visit _____) Date (day/month/year): _____ / _____ / _____

SLEDAI score (at time of screening): _____ Remission Mild Moderate Severe

Previous SLEDAI scores: _____

Diagnosis of SLE Recurrence

Clinical (SLE)	
History review	
Physical Examination	

Management of SLE Recurrence (based on rheumatologist's judgement)

- INH discontinue
- Continue INH
- Changes in SLE medications (see CRF for SLE medications, any changes should be noted on the CRF)
- Other medications: _____

SLE Recurrence Outcome

Outputs	SLEDAI Score	Date (day/month/year)
 Relapse		
 Improving		
 Active Persistent		
 Remission		
 Died		
 Others:		

CRF INH Safety Study in SLE Patients:
SLE medications

No Subject _____

Full Name: _____ Gender: F / M

Date of Birth (day/month/year): _____ / _____ / _____ Tel/Phone: _____

Visit (____ months from visit ____) Date (day/month/year): ____ / ____ / ____

Take SLE medication regularly: Yes No

SLE medications

Medicine	Dosage
 Prednisone or equivalent	mg/day
 Pulse Steroids	mg/day

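### For enzymes and SLEDAI measured at seven post-baseline visits, Data Analysis fixes unadjusted two-group tests without naming the visit or summary compared, and leaves the Visit 0 value unused as a covariate

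*Protocol*

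**What the plan says.** Data Analysis describes the safety assessment as made "by analyzing the increase in SGOT/SGPT values and assessing SLE disease activity measured using SLEDAI". The first assessment is at two weeks, "followed by monthly for the first three months (months 1, 2, 3), then every three months until one year (months 6, 9, 12"). That makes seven post-baseline visits: 0.5, 1, 2, 3, 6, 9 and 12 months. Research Design gives the same schedule, with a nine-month INH course.

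The inference is then fixed in two sentences: "Statistical tests used were t-test and/or chi-square by comparing two treatment groups" and "Results were considered significant when the p value was ≤ 0.05". The protocol names no decisive visit, per-patient summary (mean, peak or ever/never) or repeated-measures method.

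The initial screening form in Appendix 2, dated as Visit 0, records SGOT, SGPT and the SLEDAI total. Baseline could enter the analysis through the reference to an increase in enzymes and through the SLEDAI change categories in the Variables table. Nothing makes it a covariate.

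**The concern.** Each patient contributes seven values per outcome, but a two-sample t-test takes one. The protocol fixes the test and the threshold but not the value that goes in. A single visit, all visits in turn, a change score, a peak, an average or an ever/never count would each fit the text.

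This matters because the stated aim is to show that INH is safe. With the comparison open, a chance difference at one visit can be reported as harm, or one quiet visit as safety, after the data are seen.

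The second part is precision. With 60 patients the intervals around a safety result will be wide, and an unadjusted comparison makes them wider than baseline values already on the CRF would allow.

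**Working it through.** **Inputs from the protocol.** Seven post-baseline visits; p ≤ 0.05; 27 per group, raised to 30; sample size stated "with a confidence level of 95%, power 80%, and effect size 0.5". The protocol gives no correlations, so those below are assumptions shown over a range. SDs are in follow-up units (follow-up SD = 1), and normal data are assumed.

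**The plan's own figure.** If effect size 0.5 means a standardised mean difference (an assumption), a two-sided two-sample t-test at 0.05 needs 64 per group for 80% power. With 27 per group it has 44%. The stated 27 does not reproduce on this reading. That is a separate issue; it is shown here only as the unadjusted reference.

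**1. Precision at one visit.** With baseline correlation r and baseline SD s, the variance factors are:
- unadjusted: 1
- ANCOVA: 1 − r²
- change score: s² + 1 − 2rs

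The 95% half-width with 30 per arm is t × √(2 × variance / 30), with t ≈ 2.00. Power is from the noncentral t with 27 per arm and a 0.5 SD difference.

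| Analysis | Variance factor | Half-width (SD) | Power |
|---|---|---|---|
| Unadjusted | 1.00 | 0.52 | 44% |
| ANCOVA, r = 0.1 | 0.99 | 0.51 | 44% |
| ANCOVA, r = 0.3 | 0.91 | 0.49 | 47% |
| ANCOVA, r = 0.5 | 0.75 | 0.45 | 55% |
| ANCOVA, r = 0.7 | 0.51 | 0.37 | 71% |

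Example at r = 0.5: 2.00 × √(2 × 0.75 / 30) = 0.45.

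For r = 0.3, 0.5, 0.7 the change score has variance factor 1.40, 1.00, 0.60 if s = 1, and 0.95, 0.75, 0.55 if s = 0.5. It can therefore be worse than no use of baseline at all. ANCOVA is at least as precise in every case, apart from one degree of freedom.

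**2. Chance findings if every visit were tested.** Simulation of two-sample t-tests at seven visits, 30 per arm, no true effect, equal between-visit correlation:

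| Assumed correlation | 0 | 0.3 | 0.5 | 0.7 | 0.9 |
|---|---|---|---|---|---|
| At least one p ≤ 0.05 | 30% | 27% | 23% | 18% | 12% |

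At correlation 0 this agrees with 1 − 0.95⁷ = 0.302. A single named comparison gives 5%.

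**3. The averaged summary and its weak spot.** Take the mean over the six visits from 0.5 to 9 months, with between-visit correlation f and baseline correlation b. The unadjusted variance is m = (1 + 5f)/6; the adjusted variance is m − b². The last column assumes the 0.5 SD effect is present at only two of the six visits, so the mean effect is 0.5 × 2/6 = 0.167 SD. Power is with 27 per arm.

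| b / f | m | m − b² | Constant effect: adjusted v unadjusted | Two of six visits: adjusted |
|---|---|---|---|---|
| 0.3 / 0.7 | 0.750 | 0.660 | 60% v 55% | 11% |
| 0.3 / 0.5 | 0.583 | 0.493 | 73% v 66% | 14% |
| 0.5 / 0.7 | 0.750 | 0.500 | 72% v 55% | 14% |
| 0.3 / 0.3 | 0.417 | 0.327 | 88% v 80% | 18% |
| 0.5 / 0.5 | 0.583 | 0.333 | 88% v 66% | 18% |
| 0.7 / 0.7 | 0.750 | 0.260 | 94% v 55% | 22% |

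**4. Error left after the fix.** Three continuous and two binary comparisons, each at 0.05, give 1 − 0.95⁵ = 0.226 if independent.

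**The case against.** **This is SAP content.** Covariates, transformation and choice of summary are often left to a SAP, and one may exist. Silence would not be a finding. Here, however, the protocol itself fixes the test family and the threshold for a repeated outcome, so the text as it stands needs changing.

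**A reader might infer that seven tests per outcome are planned, with an inflated error rate.** The documents do not support that. Testing every visit is one of several readings the text allows, and the 12% to 30% describes that reading only.

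**A reader might infer that the unadjusted test is biased or invalid, or that baseline is ignored.** Neither follows. Under randomisation the t-test is valid, and so is a change score, which the reference to an increase may imply. What is lost is precision, and the amount depends on correlations the protocol does not give. Entry requires remission or low disease activity "with a history of stable SLE treatment in the last three months and have good liver function", which narrows baseline and may lower its correlation with follow-up. At r = 0.1 the gain is negligible. SLEDAI in such patients will also sit near zero, so the normal-theory figures are only a guide. All of this stands and limits the size of the point.

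**The average can hide a short enzyme rise or flare.** This also stands. With the effect at two of six visits, power is about 11% to 22%, against 44% for an unadjusted test at an affected visit known in advance. Nor is the event comparison a strong safeguard: with 27 per arm, chi-square power runs from about 18% (assumed risks 2% v 10%) to 42% (5% v 20%). Single-visit estimates must therefore remain visible.

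**Endpoint definitions.** The hepatotoxicity definition ("Increase of more than twice the upper limit of normal SGOT/SGPT values and improvement after drug withdrawal") and the follow-up form (≥ "2x Upper limit of normal values") differ at exactly twice the limit. The reading of drug withdrawal in a control arm that takes no INH, and the SLEDAI score against which relapse is counted, are also open. These are separate points and add no weight here.

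**Conclusion.** The point holds as a cheap improvement that should be made, with medium confidence. Data Analysis fixes valid but unadjusted tests, does not say which of seven values per patient is compared, and leaves recorded baseline values unused as covariates.

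The firm part is the open comparison: it follows from the text and needs no assumption. The gain in precision is conditional. The interval half-width narrows by about 5% at r = 0.3 (0.49/0.52), 13% at 0.5 (0.45/0.52) and 29% at 0.7 (0.37/0.52), and hardly at all at 0.1. The chance-finding figures apply only if every visit is tested.

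A reader might also infer that adjustment restores the stated 80% power. At a single visit it does not, at any correlation shown. The six-visit average exceeds 80% only for a constant effect under the equal-correlation assumptions in the table.

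**What to change.** In Data Analysis:

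1. Replace the t-tests with one baseline-adjusted comparison for each of SGOT, SGPT and SLEDAI: ANCOVA or a repeated-measures model with the Visit 0 value as covariate, and enzymes on the log scale.
2. Name one summary in advance, for example the average arm difference over the visits from 0.5 to 9 months. Report month 12, after the planned course, separately.
3. Make one chi-square or exact comparison for each binary outcome (hepatotoxicity, relapse), counting each patient once.
4. Show every single-visit difference descriptively with a 95% confidence interval.
5. Report all five comparisons with intervals, and state that five tests at 0.05 carry up to about a 23% chance of some false signal if independent.

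Separately, reconcile the places in the Variables table and Appendix 2 that define the hepatotoxicity and relapse events.

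The cost is wording and a little more analysis in SPSS or Stata, both already named; no new data or visits are needed. The limits to state are that four of the six averaged visits fall in the first three months, that the CRF allows INH to be discontinued (which can dilute the average), and that power for an effect confined to two visits is low.
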